## 1.2. Sample Size, Power, and Minimum Detectable Differences

To have power of 0.80 to detect a clinically meaningful reduction of a 2% difference in amount of trip time spent actively using a phone (72 seconds/hour of driving), the minimum sample size is 1,842 (301 per arm).

With a target sample size of 3,000 and power of 0.80, we should be able to detect a difference between treatment arms of 52 seconds/hour of driving (i.e. an absolute reduction in phone use % of 1.44%). We would have a power of 0.94 to detect a difference of 60 seconds/hour of driving.

Proposed variables to be considered as effect modifiers in the primary analysis
1. iPhone vs. Android. Hypothesis: the relative reductions in active handheld phone use will be greater among those with iPhones due to the notification to encourage Do Not Disturb While Driving.
2. Quartile of baseline period active phone use % (i.e. total active handheld phone use seconds / total trip seconds). Hypothesis: the relative reductions in active hand held phone use while be greater among those in the highest quartile of baseline phone use due to greatest opportunity for improvement and least opportunity for improvement in the lowest quartiles.
3. Proportion of period active phone use % due to handheld calls vs. handheld non-call use. Hypothesis: the relative reductions in active hand held phone use while be greater among those with a greater proportion of handheld phone use due handheld call use vs. non-call use due to multiple available technological means to switch to handsfree calls.
4. Proposed variables to be considered as effect modifiers in hypothesis generating secondary analyses
5. Baseline use of automated Do Not Disturb While Driving setting (Y/N)
6. Baseline use of a phone mount
7. Mean hours of driving/week during baseline period
8. Age
9. Sex
10. Marital status
11. Urban-suburban-rural residence
12. Residence in state with universal handheld ban
13. Income
14. Education level

15. Number of prior traffic violations in prior 5 years
16. Number of car crashes in prior 5 years
17. Self-reported frequency of types of handheld phone use while driving (e.g. phone call, text messaging, adjusting navigation app, changing music app, social media app)
18. Willingness to give up phone use while driving scale
19. Automaticity scale of phone use while driving
20. Compulsive phone use scale
21. Delay discounting rate

These estimates should be conservative as adding the rich set of baseline covariates (e.g. demographics, Apple Car Play, etc) to the model should increase the precision of the model estimates.

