## **2. TRIAL DESIGN**

### **2.1 Overview**

We propose to conduct a randomized, control trial evaluating the comparative effectiveness of social comparison and financial incentive interventions with customers of Progressive's mobile phone usage-based insurance policy. A total of 3,000 adult participants will be enrolled with 500 participants per arm. We expect an attrition rate of 17% based on historical customer data.

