#### **4.2. Sample Size, Power, and Minimum Detectable Differences**

To detect a clinically meaningful reduction of 60 seconds/hour of driving (i.e. an absolute reduction in phone use % of 1.67%), the minimum sample size is 2,406 (401 per arm).

With a target sample size of 3,000 and power of 0.80, we should be able to detect a difference between treatment arms of 52 seconds/hour of driving (i.e. an absolute reduction in phone use % of 1.44%). We would have a power of 0.94 to detect a difference of 60 seconds/hour of driving.

These estimates should be conservative as adding the rich set of baseline covariates (e.g. demographics, Apple car play, etc) to the model should increase the precision of the model estimates.

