## B. Final Statistical Analysis Plan

### 1. STATISTICAL ANALYSIS PLAN

#### 1.1. Analytic Methods

The primary outcome is **seconds of active handheld phone use per hour of driving**, which can also be expressed as active phone use %. We will use fractional regression with a logit link function as our primary analytic model to assess effectiveness between and among the 5 interventions. Specifically, we will evaluate these 10 predefined contrasts:

1. Social Comparison Feedback versus Control (monitor only)
2. End of Rating Period Incentive versus Control (monitor only)
3. End of Rating period Incentive + Social Comparison Feedback versus Control (monitor only)
4. Weekly Loss-Framed Incentive + Social Comparison Feedback versus Control (monitor only)
5. Larger Weekly Loss-Framed Incentive + Social Comparison Feedback versus Control (monitor only)
6. End of Rating Period Incentive versus Social Comparison Feedback
7. End of Rating Period Incentive + Social Comparison Feedback versus Social Comparison Feedback
8. End of Rating Period Incentive + Social Comparison Feedback versus End of Rating Period Incentive
9. Weekly Loss-Framed Incentive + Social Comparison Feedback versus End of Rating Period Incentive + Social Comparison Feedback
10. Larger Weekly Loss-Framed Incentive + Social Comparison Feedback versus Weekly Loss-Framed Incentive + Social Comparison Feedback

Although longitudinal models such as generalized estimating equations might be considered in light of the repeated trip measures among individual participants, fractional regression with a logit link is preferred in this case because the primary outcome collapses to a proportion between 0 and 1 that is weighted by travel time within and across trips. Furthermore, weekly feedback messages and incentives are delivered based on the weekly averages of seconds of active handheld phone use time divided by weekly total trip time. The model will be adjusted for: 1) length of time in the Snapshot program during the Baseline period; 2) and observed primary outcome during the Baseline period. Other covariates to be included in the model include:

1. Proposed baseline covariates to be included in primary outcome analysis model
2. Baseline period active phone use % (i.e. total active handheld phone use seconds / total trip seconds)
3. Proportion of period active phone use % due to handheld calls vs. handheld non-call use
4. Mean hours of driving/week during baseline period
5. Age
6. Sex
7. Marital status

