8. Urban-suburban-rural residence
9. Residence in state with universal handheld ban
10. Race/ethnicity
11. Income
12. Education level
13. Phone type (iPhone vs. Android)
14. Baseline use of automated Do Not Disturb While Driving setting (Y/N)
15. Bluetooth/USB car connectivity (Y/N)
16. Dashboard touchscreen (Y/N)

17. Frequency of letting passenger use phone
18. Frequency of riding as a passenger
19. Number of prior traffic violations in prior 5 years
20. Number of car crashes in prior 5 years

Due to the multiple pre-planned contrasts, we will adjust for multiple comparisons using the Holm method. First, the 10 contrasts will be ranked (lowest to highest) based on the raw p-value from the logistic regression. For a contrast to be significant using the Holm threshold, the raw p-value must be below the threshold for each row calculated as  $(0.05 / [n \text{ remaining contrasts}])$ .

Correspondingly, for clarity of presentation, adjusted p values will be reported by multiplying the raw p value by the number of remaining contrasts. For example, the smallest p-value is multiplied by 10 to obtain the adjusted p-value.

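### Final SAP 1.2: 1,842 is not six times 301, and the 72 s/h minimum, the 52 s/h detectable difference and the 0.94 power are not reproduced from any single basis tried; the inputs are unstated

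*Combined protocol and SAP*

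**What the plan says.** Final SAP 1.2 makes three statements about size and power.

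- For a 2-percentage-point difference (72 s/h) at power 0.80, "the minimum sample size is 1,842 (301 per arm".
- With 3,000 participants and power 0.80, "we should be able to detect a difference between treatment arms of 52 seconds/hour of driving".
- "We would have a power of 0.94 to detect a difference of 60 seconds/hour of driving".

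It gives no SD, control mean, alpha, sidedness or attrition allowance for these figures. Elsewhere, the protocol sets six arms of 500 and says in 2.1: "We expect an attrition rate of 17% based on historical customer data". Final SAP 1.1 says "We will use fractional regression with a logit link function as our primary analytic model" and, for the ten contrasts at a family level of 0.05, "we will adjust for multiple comparisons using the Holm method". The closing remark of 1.2 is "These estimates should be conservative as adding the rich set of baseline covariates", so covariate gain is presented as additional to the printed figures.

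Original protocol 4.2 carried the same 52 s/h and 0.94 sentences. Its minimum was for 60 s/h: "the minimum sample size is 2,406 (401 per arm". Only the minimum-sample-size sentence differs in the final SAP.

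**The concern.** The total and per-arm minimum contradict each other as printed. Beyond that, the first two statements share power 0.80, so under a common SD, alpha and N basis each determines the other, and they disagree. The third statement follows from the second under the same conditions and does not match either. Since the minimum was rewritten while the other two sentences stayed the same, the figures may come from different calculations, though the documents do not confirm this.

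At stake is whether the stated sensitivity can be checked or cited. A non-significant contrast would be read against a detectable difference of 52 s/h and a power of 0.94 at 60 s/h. A reader cannot tell which SD, Holm step or analysable number those rest on.

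**Working it through.** **Inputs.** From final SAP 1.2: 72 s/h, 1,842 and 301 at power 0.80; 52 s/h at 3,000 and power 0.80; power 0.94 at 60 s/h. From protocol 2.1: 500 per arm and 17% attrition. From protocol 2.9: six arms. From final SAP 1.1: Holm over ten contrasts, so the first step is 0.05 / 10 = 0.005. The SD is not given. It cancels in steps 2 to 4.

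**Step 1: total against per-arm.** 6 × 301 = 1,806; 1,842 / 6 = 307. The gap is 36 participants (2%). The pair in original protocol 4.2 does multiply: 6 × 401 = 2,406.

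**Step 2: 72 s/h against 52 s/h.** For two equal arms, n = 2 × SD² × (z_alpha + z_power)² / difference². With the same SD, alpha, sidedness and power, n × difference² is constant.

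- From 52 s/h at 500: n for 72 s/h = 500 × (52/72)² = 260.8, about 261 per arm. Letting 52 stand for 51.5 to 52.5 gives 256 to 266. Neither 301 nor 307 is reached.
- From 301 per arm: detectable difference at 500 = 72 × √(301/500) = 55.9 s/h. From 307: 72 × √(307/500) = 56.4 s/h.

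**Step 3: power at 60 s/h with 500 per arm.** Power = Φ[(z_alpha + 0.842) × (60/d) × √(500/n) − z_alpha], where d at n per arm is the pair with power 0.80. Here z_alpha = 1.960 for two-sided 0.05 and 2.807 for 0.005.

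| Basis | Two-sided 0.05 | Two-sided 0.005 |
|---|---|---|
| 52 s/h at 500 | Φ(2.802 × 1.154 − 1.960) = 0.898 | 0.920 |
| 72 s/h at 301 | 0.853 | 0.867 |
| 72 s/h at 307 | 0.846 | 0.858 |

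The printed value is 0.94.

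**Step 4: can attrition reconcile them?**

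- Inflate only the minimum: 260.8 × 1.17 = 305, or 260.8 / 0.83 = 314. Reversed, 307 / 1.17 = 262, which gives 52.2 s/h at 500. The 72 and 52 s/h figures then roughly agree, but power at 60 s/h is 0.897 (0.05) or 0.918 (0.005).
- Take 52 s/h at the number evaluable, and 60 s/h at 500. Evaluable is 500 × 0.83 = 415 or 500 / 1.17 = 427. At two-sided 0.05 with constant SD, power is 0.944 or 0.938, both rounding to 0.94. The 72 s/h minimum is then 415 × (52/72)² = 217 or 427 × (52/72)² = 223 evaluable, which is about 261 enrolled either way. Step 2's mismatch remains.
- Apply one attrition basis throughout: it cancels, and steps 2 and 3 are unchanged.

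**Step 5: can a log-odds test reconcile them?** Assume a control mean of 4% (not in the documents) and constant outcome variance. The SE of a log-odds difference is proportional to √{1/[p₀(1−p₀)]² + 1/[p₁(1−p₁)]²}.

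- 52 s/h: p₁ = 0.0256, log-odds difference 0.463, SE factor 47.9, ratio 0.00967.
- 72 s/h: p₁ = 0.0200, log-odds difference 0.714, SE factor 57.3, ratio 0.01246.
- n for 72 s/h = 500 × (0.00967/0.01246)² ≈ 301.

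This matches 301, but power at 60 s/h is then 0.88 (0.05) or 0.90 (0.005), not 0.94.

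**The case against.** The strongest reply is that 1.2 may be right on a basis it does not print. The primary model has a logit link, and step 5 shows one log-odds setting on which 301 and 52 s/h agree. Step 4 shows a simple route to 0.94 with constant SD at two-sided 0.05. Some log-odds settings that also use different attrition bases for different figures match all three, at assumed control means of 2.2% to 4.2%. This stands: the documents do not prove that the figures are irreconcilable. But each route needs inputs that 1.2 does not give, and the three-way matches also need attrition handled differently within one section.

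A reader might infer that 0.94 has been shown to be wrong. The documents do not support that, because the SD, alpha step and evaluable number behind it are unknown.

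A reader might also infer that the trial is underpowered. That is not supported either. The target of 3,000 is above every minimum discussed, and a detectable difference near 56 s/h is still below both 60 and 72 s/h. No test or decision rule in final SAP 1.1 uses these numbers, and the 36-participant gap may be a slip in one digit.

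**Conclusion.** The point holds as a minor reporting error. The disagreement between 1,842 and 301 needs only the six equal arms. The mismatch between 261 and 301 to 307 per arm (equivalently, 52 against about 56 s/h) rests on a common SD, alpha and N basis and does not depend on their values. The printed minimum is 15% to 18% above what the 52 s/h figure implies (301/261 and 307/261).

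The 0.94 is doubtful rather than refuted: 0.90 to 0.92 on the 52 s/h basis and 0.85 to 0.87 on the 301 to 307 basis, with constant SD and a shared N. No single basis tried gives all three figures. That describes the bases tried and does not prove that none exists.

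**What to change.** Recompute every figure in final SAP 1.2 from one calculation and state its inputs:

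- the SD, or a variance model with a control mean;
- the test scale (s/h difference or log-odds);
- the alpha step (0.05 or the first Holm step, 0.005) and sidedness;
- whether N means enrolled or evaluable after 17% attrition.

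Correct the total or the per-arm minimum so that they multiply by six, and restate the 52 s/h and 0.94 figures from that same calculation. The values worked out above illustrate the mismatch and should not be printed as replacements, because the documents do not give the SD or control mean.

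The cost is SAP wording only, with no change to enrolment or analysis. The downside is that the stated detectable difference and power may become slightly less favourable.

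### SAP 1.2 states power for 52 and 60 s/h without alpha, SD or any allowance for Holm over ten contrasts; if it means one two-sided 0.05 test, power for 52 s/h under the SAP's own rule is about 0.5–0.7

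*Combined protocol and SAP*

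**What the plan says.** Final SAP 1.1 names ten contrasts as the primary analysis and then states: "Due to the multiple pre-planned contrasts, we will adjust for multiple comparisons using the Holm method". The contrasts are ranked by raw p-value. Each p-value is compared with 0.05 divided by the number of contrasts remaining, and the smallest is multiplied by 10. The thresholds therefore run from 0.005 up to 0.05, and 0.05 applies only to the last contrast, after the other nine have been rejected.

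Final SAP 1.2 gives the power at 3,000 participants: "With a target sample size of 3,000 and power of 0.80, we should be able to detect a difference between treatment arms of 52 seconds/hour". It adds: "We would have a power of 0.94 to detect a difference of 60 seconds/hour of driving". For its clinically meaningful difference of 72 s/h at power 0.80 it says "the minimum sample size is 1,842 (301 per arm". It closes with "These estimates should be conservative as adding the rich set of baseline covariates", and offers no other reason for calling the figures conservative.

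No alpha, sidedness, SD, test or multiplicity allowance accompanies these figures. Protocol 4.2 prints the same 52 and 60 s/h figures with the same gap. Protocol 2.1 says "A total of 3,000 adult participants will be enrolled with 500 participants per arm" and expects 17% attrition. Neither document says whether that attrition enters the power figures.

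**The concern.** Power is useful only if it is the chance of passing the test that will be applied. Here the test is Holm over ten contrasts, while the power sentence speaks of a difference between two arms and never mentions the ten contrasts or a reduced level. The only 0.05 in the SAP is the numerator of the Holm threshold.

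A reader will take 0.80 at 52 s/h and 0.94 at 60 s/h as the chance that a planned contrast is declared significant. If the figures are for an unadjusted test, that chance is overstated. The contrasts between active arms (6 to 10) are the most exposed: a non-significant result there could be read as showing that two interventions perform alike, when the trial could not reliably separate them at that size.

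**Working it through.** **Inputs.** From the documents: 500 per arm; 0.80 at 52 s/h; 0.94 at 60 s/h; 0.80 at 72 s/h with 301 or 307 per arm (1,842/6 = 307, while 6 × 301 = 1,806); Holm over ten contrasts from 0.05; 17% attrition, which would leave 500 × 0.83 = 415 per arm. Assumed: two-sided tests, a common SD, the normal approximation, and a per-test alpha of either 0.05 or 0.005.

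**Formulas.** Power = Φ(δ/SE − z), with SE = SD × √(2/n). The critical value z is 1.960 at 0.05 and 2.807 at 0.005. Power 0.80 needs δ/SE = z + 0.842.

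**1. Reproducing the stated figure.** 0.80 at 52 s/h cannot be derived independently, because neither alpha nor SD is given. It can only be used to back-solve the SD:
- alpha 0.05: SD = 52/(1.960 + 0.842) × √250 ≈ 293.5 s/h
- alpha 0.005: SD = 52/(2.807 + 0.842) × √250 ≈ 225.3 s/h

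**2. First Holm step on the 0.05 reading.** At 52 s/h, δ/SE = 2.802.
- 52 s/h: Φ(2.802 − 2.807) = 0.498
- 60 s/h: Φ(2.802 × 60/52 − 2.807) = 0.665
- 72 s/h: Φ(2.802 × 72/52 − 2.807) = 0.858
- Difference with power 0.80: 52 × (2.807 + 0.842)/2.802 = 67.7 s/h

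**3. Full Holm procedure.** Simulation of 200,000 trials, with six arm means, 500 per arm and the SAP's ten contrasts with their correlations. The table gives power for each contrast whose true size is 52 s/h.

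| True effects of Arms 2–6 vs control (s/h) | SD 293.5 (0.05 reading) | SD 225.3 (0.005 reading) |
|---|---|---|
| Arm 6 only: 52 | 0.50–0.51 | 0.81 |
| Arm 2 only: 52 | 0.51 | 0.81 |
| All five: 52 | 0.53 | 0.83 |
| Arms 3–6: 52 | 0.54 | 0.84–0.85 |
| 52/52/104/156/208 | 0.63–0.64 | 0.91–0.92 |
| 52/104/156/208/260 | 0.71–0.72 | 0.95 |

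On the 0.05 reading no simulated pattern reaches 0.80. On the 0.005 reading every pattern does.

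**4. Do the printed figures identify the alpha?** Starting from 0.80 at 52 s/h, power at 60 s/h is:
- alpha 0.05: Φ(2.802 × 60/52 − 1.960) = 0.898 (0.893–0.904 if 52 is a rounded value between 51.5 and 52.5)
- alpha 0.005: Φ(3.649 × 60/52 − 2.807) = 0.920 (0.914–0.926)

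Neither gives 0.94. Solving the pair exactly needs a two-sided alpha near 0.00015, or at most about 0.0012 after rounding. No such level appears in the documents.

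**5. The 72 s/h sizing.** At 0.80, n per arm for 72 s/h scales to a detectable difference at 500 per arm of 72 × √(n/500). This is 55.9 s/h for n = 301 and 56.4 s/h for n = 307, whatever the alpha, against the printed 52. Power for 52 s/h at 500 per arm is then 0.73–0.74 (alpha 0.05) or 0.71–0.72 (alpha 0.005).

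**6. Covariate gain needed.** To restore 0.80 for 52 s/h at 0.005 on the 0.05 reading, residual variance must fall to (2.802/3.649)² = 0.59 of the total, so the covariates must explain about 41%.

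**The case against.** The strongest objection is that the unadjusted 0.05 is inferred. The SAP never says that SAP 1.2 used it, and the 0.05 in SAP 1.1 is the family-wise level. The printed pair leans slightly the other way: 0.80 at 52 s/h gives 0.920 at 60 s/h under 0.005 and 0.898 under 0.05, so the stricter level lies nearer to 0.94. This stands. A reader might infer that the SAP demonstrably reports unadjusted power, or that true power is 0.50 rather than 0.80. The documents support neither. Nor does the pair show that Holm was built in, since neither level reproduces 0.94. A mixed reading could also explain it: 52 s/h computed at 415 per arm and 60 s/h at 500 per arm, both at 0.05, gives 0.944.

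The size also depends on which figure is trusted. Setting the SD from 0.94 at 60 s/h at alpha 0.05 (SD 269.9) gives 0.59 for 52 s/h at the first step. Under Holm it gives 0.60–0.69 for most patterns and 0.81–0.82 for the strict 52 s/h ladder.

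The primary model adjusts for baseline phone use and many covariates, which these figures leave out. That gain could offset the Holm loss. The documents give no correlation or explained variance to show it, so the description of the estimates as conservative is unproven rather than wrong.

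Finally, a reader might infer that 72 s/h is safely covered under Holm because step 2 gives 0.858. On the 0.05 reading that does not hold up. It falls to about 0.77 at 415 per arm, and to 0.78–0.79 at 500 per arm with the SD (315–318 s/h) implied by the SAP's own 72 s/h sizing.

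**Conclusion.** The concern holds in conditional form. SAP 1.2 does not connect its power figures to the Holm rule that defines significance, and it omits the inputs needed to tell whether they apply. If they are for one two-sided 0.05 test, a true 52 s/h contrast has power of about 0.5–0.7 on the SD implied by 0.80 at 52 s/h, with 500 per arm and no covariate gain. It would be missed about 30–50% of the time instead of 20%. The spread reflects the pattern of true arm effects and is not a strict bound. If 0.005 was used, there is no shortfall at 52 s/h.

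This is more than missing detail, because the 52, 60 and 72 s/h figures do not fit together at either level. At least one needs correcting whichever alpha was used. The correction changes no estimate, test or decision rule. It changes what a non-significant contrast can be taken to mean.

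**What to change.** In SAP 1.2 the sponsor should:
- state the alpha, sidedness and SD behind the power figures, and whether the 17% attrition is included;
- recompute power and the detectable difference for the Holm-adjusted test from the actual SD, and replace the 52 and 60 s/h sentences with the results;
- reconcile the 72 s/h sizing, including 1,842 against 301 per arm, with the same inputs;
- label any figure at unadjusted 0.05 as such;
- keep the description of the estimates as conservative only if the covariate gain is shown to offset the Holm loss (about 41% of variance explained on the 0.05 reading).

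The values 68 s/h, 0.50, 0.67 and 0.86 illustrate the assumed SD of about 293 s/h and should not be written into the SAP. If 0.005 was used, a sentence saying so settles the Holm question, though the figures still have to be reconciled.

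The cost is one recalculation and a few sentences. The downside is a possibly less favourable stated detectable difference. No change in enrolment is proposed.

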### **1.3. Subgroup Analyses, Effect Modification, and Mediation Analysis**

For the 10 pre-defined contrasts, we will also assess the effect modification of having an iPhone versus Android phone. This will enable us to estimate the effectiveness of push notifications to encourage the automated activation of Do Not Disturb While Driving. These notifications only get sent to iPhones. In the primary analysis, we will also determine the extent to which relative reductions in phone use are modified by the amount of baseline phone use.

We will also conduct a mediation analysis to determine whether activation of an automated Do Not Disturb While Driving setting during the trial as measure on intake and exit surveys mediates the primary outcome by treatment arm and by phone type.

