## **2.9. Allocation to Treatment**

Progressive Snapshot users that opt-in to participate will be added to a study list tracked by TrueMotion. 3,000 participants have enrolled into the study, they will complete an intake survey, collecting information about driving history, demographics, and behavioral characteristics. Simple individual-level randomization will be used. TrueMotion will use a random number generator to randomize each user that opts in to 1 of the 6 arms: (Arm 1) control, (Arm 2) social comparison feedback, (Arm 3) end of rating period incentive, (Arm 4) end of rating period incentive and social comparison feedback (Arm 5) weekly loss framed incentive and social comparison feedback, (Arm 6) larger weekly loss framed incentive and social comparison feedback. Intervention will be delivered by TrueMotion through the Snapshot mobile app to the study participants. Additionally, iPhone users in all arms will get push notifications prompting them to activate the Do Not Disturb While Driving setting on iPhones.

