## **2.10. Behavioral Interventions**

### **2.10.1. Intervention Arms**

Intervention Arm	Notifications	Incentive	
		Timing	Size
Driver Mode Nudge (all arms, iPhone users only)	3 times over 3 weeks: Prompt to enable Do Not Disturb While Driving. Linked to website with instructions and frequently asked questions: www.besafir.org/do-not-disturb .  Sample messages: Arms 1-2: "Reduce annoying notifications when driving (while keeping the urgent ones!). Enable Do Not Disturb While Driving. Tap here to learn how!"  Arms 3-6: "Increase your chance to earn \$ and reduce annoying notifications when driving (while keeping the urgent ones!). Enable Do Not Disturb While Driving. Tap here to learn how!"	N/A	N/A
1. Control (monitor only)	Continue in monitoring only mode	N/A	N/A
2. Social comparison feedback	Initial push notification: Told they will be compared to drivers like them each week and that they will receive up to 3 stars.	N/A	N/A

	
Weekly push notification:
 
a. Compare phone use % relative to Progressive Snapshot customers like them based (age, sex, marital status, urban/suburban/rural residence). Told can receive up to three stars.
 
 
• 1 star (if <50th percentile)
 
• 2 stars (if <math>\geq</math> 50th percentile, <90th percentile)
 
• 3 stars if <math>\geq</math> 90th percentile (top performer)
 
 
Sample message: “★ ★ out of 3 stars. Almost there! You're better than at least half of our drivers at staying off your phone. A little less swiping, typing, and holding the phone and you'll be one of our best drivers! ”
		
3. End of rating period incentive	
Initial notification:
 
a. Financial Incentive: Tell them they have a chance to win \$50 in 50 days for keeping handheld phone use to a minimum.
 
 
• If <50th percentile), then paid \$0
 
• If <math>\geq</math> 50th percentile, <90th percentile), then paid \$25
 
• If <math>\geq</math> 90th percentile (top performer), then paid \$50
 
	Redeemed at end of rating period	Max: \$50 (\$1/day)

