## 2.11. Assessment Controls

Participants allocated to the control arm that have iPhones will receive push notifications prompting them to enable Do Not Disturb While Driving once a week for 3 weeks, without receiving any feedback or goal support for the intervention period, 50 days.

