#### **4.3. Subgroup Analyses and Effect Modification**

For the 10 pre-defined contrasts, we will also assess the effect modification of having an iPhone versus Android phone. This will enable us to estimate the effectiveness of push notifications to enable automated activation of Do Not Disturb While Driving. These notifications only get sent to iPhones.

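### Phone-type effect modification cannot estimate whether the Do Not Disturb prompt works, because every iPhone user in every arm is prompted and no Android user is

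*Combined protocol and SAP*

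**What the plan says.** SAP 1.3 assesses phone type as an effect modifier of the 10 pre-defined contrasts and gives the purpose: "This will enable us to estimate the effectiveness of push notifications to encourage the automated activation of Do Not Disturb While Driving". Protocol 4.3 makes the same claim: "This will enable us to estimate the effectiveness of push notifications to enable automated activation of Do Not Disturb While Driving". SAP 1.2 lists phone type first among the effect modifiers for the primary analysis, with a directional hypothesis: "the relative reductions in active handheld phone use will be greater among those with iPhones due to the notification".

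The delivery of the prompt is described elsewhere. Protocol 2.9 states that "iPhone users in all arms will get push notifications prompting them to activate the Do Not Disturb While Driving setting on iPhones". The intervention table in Protocol 2.10.1 likewise applies it to every arm but to iPhone users alone. Protocol 2.11 confirms it for controls: "Participants allocated to the control arm that have iPhones will receive push notifications prompting them to enable Do Not Disturb While Driving". SAP 1.3 itself notes that only iPhones receive these messages. The sample wording differs by arm: in arms 3-6 it opens with "Increase your chance to earn", which the version for arms 1-2 lacks.

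Only arm is randomised. SAP 1.1 includes phone type as a covariate. SAP 1.3 adds a mediation analysis of whether activating the setting "mediates the primary outcome by treatment arm and by phone type".

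**The concern.** An effect can be estimated only if some comparable people are exposed and others are not. Here no iPhone user goes unprompted and no Android user is prompted. Each of the 10 contrasts compares two arms whose iPhone users were all prompted, so the difference between arms has already removed whatever the prompt does in both.

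The risk is misreading in both directions. A null interaction could be reported as showing that the prompt does not work. An interaction in the hypothesised direction could be credited to the prompt when it reflects some other difference between iPhone and Android users. The plan invites both readings by attaching the prompt question to a modifier in its primary analysis.

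**Working it through.** The documents give no sample size, power or alpha for this interaction, so there is no planned figure to reproduce. The question is what the interaction identifies.

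**Aliasing.** The arm-by-phone layout has 6 × 2 = 12 cells. The model with intercept, five arm terms, phone type and five phone-by-arm terms has 12 columns and rank 12. Adding a prompt indicator gives 13 columns, but the rank stays at 12, because prompt equals iPhone in every cell. If some iPhone users were unprompted, the 13 columns would have rank 13. More participants do not change this.

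**What the interaction contains.** On the logit scale of SAP 1.1, write

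logit p = a + d·(iPhone) + t(arm) + w·(iPhone in arms 3-6),

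where d is the prompt effect common to all arms, t the arm effect and w the extra effect of the earning message. For arm g against arm h:

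interaction = [(a + d + t_g + w_g) − (a + d + t_h + w_h)] − [t_g − t_h] = w_g − w_h.

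- Contrasts 1, 8, 9 and 10: both arms have the same sample wording, so the interaction is 0.
- Contrasts 2-7: an arm from 3-6 is set against arm 1 or 2, so the interaction is w. With w = -0.1 it is -0.1 whether d is 0 or -0.5.
- d appears in neither.

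The zeros follow from defining d as the common part. The point is that no value of d can be recovered.

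**The relative scale, which SAP 1.2 uses.** The documents supply no inputs, so these are assumptions: control use of 3%, 6% or 10%; arm odds ratio (OR) 0.80 or 0.60; d = 0, -0.22 or -0.5; w = 0. For example, at 6% and OR 0.80 with d = 0, the odds are 0.06/0.94 = 0.0638. Multiplied by 0.80 they are 0.0511, which is a proportion of 0.0486, a relative reduction of 1 − 0.0486/0.06 = 19.0%.

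| Control use | Arm OR | d = 0 | d = -0.22 | d = -0.5 |
|---|---|---|---|---|
| 3% | 0.80 | 19.5% | 19.6% | 19.7% |
| 6% | 0.80 | 19.0% | 19.2% | 19.4% |
| 10% | 0.80 | 18.4% | 18.7% | 19.0% |
| 3% | 0.60 | 39.3% | 39.4% | 39.6% |
| 6% | 0.60 | 38.5% | 38.8% | 39.1% |
| 10% | 0.60 | 37.5% | 38.0% | 38.4% |

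The largest movement across a row is 0.9 points. A useless prompt and a strong one look almost the same.

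**The converse.** Set the prompt effect to 0 and let all five interventions work 0.1 log-odds better on iPhones for some other reason. The interaction is then -0.1 on each of the five contrasts with control.

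**The absolute scale.** With 6% control use, arm effects of 0 to -0.30, a 0.1 log-odds phone-type difference and prompt effects of 0 to -0.6 (all assumed), the logit link alone produces interactions of about -5 to +20 s/h. These do not estimate the prompt effect either.

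**The case against.** **SAP 1.2 may mean reduction from baseline.** On that reading, a larger fall in iPhone users because of the prompt is a coherent idea. But the item sits in a list of effect modifiers, and SAP 1.3 ties phone type to the 10 between-arm contrasts. A change-from-baseline comparison by phone type is a different, non-randomised analysis that the SAP does not specify. If it was intended, it has to be written down.

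**Prompt wording and prompt-by-arm synergy could create an interaction.** True, and either could motivate a directional hypothesis. A wording effect is possible only in contrasts 2-7; synergy is possible in any contrast. Neither measures prompt against no prompt, and neither can be separated from other iPhone/Android differences.

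**Other planned analyses might fill the gap.** The mediation analysis concerns survey-reported activation of the setting, not receipt of the prompt. The phone-type covariate mixes the prompt with everything else that differs between the two groups. Neither supplies unprompted iPhone users.

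**A control-arm comparison has the same aliasing.** This stands: it supplies no unprompted iPhone group either. It is defensible only as an optional, labelled estimate with its assumption stated. Arm 2 has the same sample wording, so restricting it to controls is a choice.

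**The consequence is limited.** This also stands. The interaction remains a valid check of whether arm effects differ by phone type; only its interpretation fails.

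**Conclusion.** The statement in SAP 1.3 and Protocol 4.3 is wrong as written. Prompt and phone type coincide in every cell, so the interaction on the 10 contrasts carries no information about the common prompt effect. That conclusion rests on the delivery rules in the documents and the logit link; the assumed inputs only illustrate the relative and absolute scales. The attribution to the prompt in SAP 1.2 cannot be tested by that interaction. The 10 primary contrasts, the Holm adjustment and the sample size are untouched. The change should be made, because it determines what may be concluded from a pre-specified modifier.

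**What to change.** Delete the sentence on prompt effectiveness in SAP 1.3 and its counterpart in Protocol 4.3, and remove the attribution to the notification from the hypothesis in SAP 1.2. Report the interaction only as effect modification by phone type.

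If the prompt is of interest, pre-specify the baseline-adjusted iPhone-Android difference within the control arm. With control as the reference and phone-by-arm terms included, this is the phone-type coefficient of the planned model. It is a log-odds ratio, so stating it in s/h needs a standardised prediction that the SAP does not describe. Label it non-randomised and state its assumption: without the prompt, iPhone and Android controls with the same baseline covariates would have had the same use (parallel trends, if change from baseline is used).

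The cost is wording in three places and one labelled coefficient. The drawback of the optional estimate is low precision:

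- SD implied by the plan's 52 s/h at 500 per arm and power 0.80 is 52 × √(500/2) divided by 2.80 or 3.65. This gives 294 s/h at two-sided alpha 0.05 and 225 s/h at 0.005; the power section states no alpha.
- SE = SD × √(1/(n·p) + 1/(n·(1 − p))), with n = 500 controls, or about 415 after the expected 17% attrition, and an assumed iPhone share p of 50-70%. The range is 20.2 s/h (SD 225, n = 500, p = 0.5) to 31.4 s/h (SD 294, n = 415, p = 0.7).
- Multiplying by 2.80 gives a detectable difference of about 56-88 s/h, before any gain from baseline adjustment.

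The lower end mixes alphas: 0.005 to derive the SD and 0.05 for the new test. With one alpha for both, the range is 52 × √2 = 74 s/h to 52 × 1.69 = 88 s/h, which is the fairer comparison with the plan's 52 s/h.
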